6. STUDY ASSESSMENTS AND PROCEDURES

The schedule of study assessments is shown in [Table 1](#) and [Table 2](#). Detailed procedures for each assessment are provided in the SRM.

Table 1 Time and Events Table

| Procedures ^{1,2} | Screening ³ | Randomization ³ /Baseline (can be same day as Screening Visit) | Study Drug Check Phone Call (4-6 wks post rand.) | Clinic Visit Month 4 ± 18 days then every 4 months ± 18 days throughout the study | Unscheduled dose adjustment visit (if warranted) | Final study clinic visit ⁴ (or early withdrawal) | Follow up Phone Call 5 ± 1 weeks after last IP dose |
|--|------------------------|--|--|---|---|--|--|
| Written informed consent | X | | | | | | |
| Review of Inc/excl criteria | X | X | | | | | |
| Demography & directed medical history | X | | | | | | |
| Assessment of MACE and micro-vascular events | | | | X | | X | |
| HbA1c | X ⁵ | | | X | | X | |
| Serum creatinine (eGFR) | X ⁵ | | | X (alternate visits) ² | | X | |
| Liver Function Tests (LFTs) ⁶ | | X | | X (alternate visits) ² | | X | |
| Record available information on most recent lipid assessment ⁷ | | X | | X (annually) | | X | |
| Genetic sampling ⁸ | | X | | | | | |
| Patient reported outcomes questionnaires ⁹ | | X ¹⁰ | | X (alternate visits) ² | | X | |
| Key concomitant non-diabetes medication | | X | | X | | X | X |
| Diabetes medication | | X | | X | | X | X |
| Study drug reminder | | | X | X | X | | |
| Physical examination ¹¹ | | X | | X (alternate visits) ² | | X | |
| SAEs, AEs of special interest, AEs leading to IP discontinuation | | X | X | X | X | X | X |
| Pregnancy test ¹² | X | X | | | | | |
| Study drug dispense/compliance ¹³ | | X | | X | X | X | |

- Subjects who discontinue investigational product should be handled as described in Section 4.4 and Section 4.5 and in Table 2.
- Assessments at month 8, 16, 24 etc. will include patient reported outcomes questionnaires, serum creatinine (eGFR), LFTs and physical examination. Those at months 4, 12, 20 etc do not.
- Screening and Randomisation can occur at the same visit if all eligibility information is available. If Screening and Randomisation occur at the same visit assessments should not be duplicated.
- Once it is projected that the target number of MACE events will have been collected and that the projected median duration of subject follow-up is at least 1.5 years, a 3 month window will be defined for conducting the final, face to face visit.

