|---|--|--|--|---|---------------------------------------|
| Assessment of MACE and micro-vascular events | X | | X | X | X |
| HbA1c | X | | | X | X |
| Serum creatinine (eGFR) | X | | | X | X |
| Liver Function Tests (LFTs) ⁵ | X | | | X | X |
| Record available information on most recent lipid assessment ⁶ | X | | X (annually) | X (annually) | X |
| Patient reported outcomes questionnaire ⁷ | X | | | | |
| Key concomitant non-diabetes medication | X | X | X | X | X |
| Diabetes medication | X | X | X | X | X |
| Physical examination ⁸ | X | | | X | X |
| AEs leading to IP discontinuation | X | | | | |
| SAEs, AEs of special interest, | X | X | X | X | X |
| Study drug compliance | X | | | | |

1. After subjects permanently discontinue IP, follow-up should continue on the 4-monthly schedule established at randomisation.
2. Where a subject would have been scheduled to attend clinic at months 4, 12, 20, 28 etc after randomisation, a telephone contact will be performed instead (with assessments as shown above).
3. Where a subject would have been scheduled to attend clinic at months 8, 16, 24, 32 etc after randomisation, a clinic visit will be performed (with assessments as shown above). If a subject who has permanently discontinued IP is unable to attend clinic then they will be contacted by telephone instead and the telephone contact assessments will be performed.
4. Once it is projected that the target number of MACE events will have been collected and that the projected median duration of subject follow-up is at least 1.5 years, a 3 month window will be defined for conducting the final, face to face visit.
5. Liver function tests: ALT, AST, alkaline phosphatase, bilirubin, GGT.
6. Lipid values (TC, LDLc, HDLc, Tg) to be recorded as available from routine clinical care annually. If results are unavailable, lipids tests are not to be performed for the study.
7. TRIM-D, EQ-5D and study specific questionnaire (details in Section 6.3).
8. See Section 6.2.7.

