6.3. Value Evidence and Outcomes

6.3.1. Value Evidence and Outcomes Assessments

6.3.1.1. Treatment Related Impact Measure – Diabetes (TRIM-D)

In order to evaluate satisfaction with treatment and to compare satisfaction across treatment groups, the TRIM-D questionnaire will be self administered by all subjects at baseline (except for subjects whose diabetes is treated by diet and exercise alone) and all subjects at each 8 month visit (and, to the extent possible, at the time of study completion or withdrawal from the study).

The TRIM-D, developed in 2009, is a 28-item treatment satisfaction measure scored to produce 5 sub-scale scores (Treatment Burden, Daily Life, Diabetes Management, Psychological Health, and Compliance) as well as a total score. It is available in a wide range of translations.

The TRIM-D development, in accordance with the principles of the Food and Drug Administration Patient Reported Outcome Guidance document, was based on findings from the published literature including content from already-existing treatment satisfaction measures as well as significant input from subjects with type 1 and with type 2 diabetes and from expert diabetes clinicians. The TRIM-D has been evaluated in a sample of 507 subjects (74% with type 2 diabetes) and has been shown to have acceptable reliability and validity [Brod, 2009a]. Its responsiveness was also evaluated in a sample of 242 subjects (71% with type 2 diabetes) and found to be acceptable [Brod, 2009b]. Some preliminary work has been done on estimating its minimal important difference but this needs further exploration [Brod, 2009b].

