6.3.1.2. EQ-5D

The EQ-5D will be self-administered by subjects in order to measure generic health status. Combining the EQ-5D with the disease-specific TRIM-D, which is designed to have maximum sensitivity to relevant aspects of disease related treatment, will provide a more robust evaluation of the impact of treatments for type 2 diabetes and allow for clearer interpretation of study results. TRIM-D results, if consistent with the general trends seen in the EQ-5D, will have enhanced credibility.

The EQ-5D is a standardized instrument used to evaluate generic health-related quality of life. It is applicable to a wide range of health conditions and treatments, and it provides a simple descriptive profile and a single index value for health status. It is also used to provide utilities, or preference weights, for use in economic (cost effectiveness) evaluations. It is available in 141 self complete official language versions.

The EQ-5D has been used extensively in studies to measure the impact of type 2 diabetes and treatments for the disease. A systematic review identified 54 publications reporting EQ-5D responses and 39 papers presenting evidence on the measurement properties of the EQ-5D in this population [Janssen, 2011]. This evidence supported the validity, reliability, and responsiveness of the EQ-5D for evaluating health-related quality of life in subjects with type 2 diabetes. Other studies reported that index scores from the EQ-5D

have been shown to be an independent predictor of the risk of mortality, future vascular events, and other complications in people with type 2 diabetes [Clarke, 2009]. In addition, the SHIELD longitudinal study (1,741 respondents with type 2 diabetes and 4,543 without diabetes) used the EQ-5D to assess the 5-year changes in health-related quality of life in type 2 diabetes [Grandy, 2012].

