8.3.6.5. Value Evidence and Outcomes Analyses

TRIM-D total score and score for each domain will be summarized descriptively by treatment group and scheduled visit. Score changes from baseline will be compared between treatments for each visit by an ANCOVA model.

For EQ-5D, subjects' responses at each visit for the 5 domains will be summarized categorically by treatment group, together with the summary of utility score at each visit and change from baseline by treatment group. Change from baseline will be compared between treatment groups for each visit by an ANCOVA model.

For study specific PRO questions, responses will be summarized descriptively by treatment group and scheduled visit.

Healthcare resource use will be summarized by treatment group and visit.

Further analysis details will be provided in the RAP.

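### Table 2 stops the patient-reported questionnaires once investigational product is permanently discontinued, which contradicts Section 6.3.1.1 for TRIM-D and leaves a gap in the each-visit comparison for EQ-5D

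*Protocol*

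**What the plan says.** Table 1 of the protocol, in its first footnote, hands discontinuers over to a separate schedule: "Subjects who discontinue investigational product should be handled as described in Section 4.4 and Section 4.5 and in Table 2". In Table 2 the questionnaire row begins "Patient reported outcomes questionnaire ⁷ | X". That single mark is in the column for the clinic visit soon after permanent discontinuation, and the other cells of the row are empty. The row's footnote defines its content as "TRIM-D, EQ-5D and study specific questionnaire (details in Section 6.3".

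Clinic attendance does not stop. A further footnote to Table 2 says that "at months 8, 16, 24, 32 etc after randomisation, a clinic visit will be performed", and HbA1c, serum creatinine, liver function tests and physical examination are marked both there and at the final visit.

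Section 6.3.1.1 sets the TRIM-D schedule as "all subjects at each 8 month visit (and, to the extent possible, at the time of study completion or withdrawal from the study". The only exemption it names is the baseline form for subjects managed by diet and exercise alone. Section 6.3.1.2 is silent on timing: "The EQ-5D will be self-administered by subjects in order to measure generic health status".

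Section 2 lists TRIM-D/EQ-5D among the secondary endpoints. For TRIM-D, Section 8.3.6.5 states: "Score changes from baseline will be compared between treatments for each visit by an ANCOVA model". It gives the same treatment to change in EQ-5D.

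**The concern.** A site cannot follow both Table 2 and Section 6.3.1.1 for a subject who is off IP and in the clinic at, say, month 16. If it follows Table 2, whether a score exists at a scheduled visit depends on something that happens after randomisation, namely whether the subject is still on IP. The comparison at that visit is then no longer between the groups as randomised. Elsewhere the protocol takes the opposite line: Section 3.3 says that subjects who stop study medication are followed to the end of the study.

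This is a matter of data collection, not of analysis detail. A later analysis plan can model or impute, but it cannot recover scores that nobody was asked for. Section 6.3.1.2 also describes EQ-5D as a source of utilities for economic evaluation, and these would be absent after discontinuation.

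**Working it through.** **Schedules side by side, for a subject who has permanently stopped IP**

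| Contact | Table 2: questionnaires | Table 2: HbA1c, creatinine, liver tests, examination | Section 6.3.1.1: TRIM-D |
|---|---|---|---|
| Clinic visit soon after stopping | marked | marked | not named as such |
| Telephone call about 5 weeks after last dose | blank | blank | not required |
| Telephone contact, months 4, 12, 20 and so on | blank | blank | not required |
| Clinic visit, months 8, 16, 24 and so on | **blank** | marked | **required** |
| Final study clinic visit | **blank** | marked | **required where possible** |

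The telephone rows raise no issue: Table 1 also has no questionnaires at months 4, 12 and 20. The conflict is in the last two rows, where the subject is in the clinic.

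**By instrument.** For TRIM-D the conflict is direct. For EQ-5D there is nothing in Section 6.3.1.2 to contradict; Table 2 is the only rule for subjects off IP, and the shortfall is against the each-visit comparison in Section 8.3.6.5. The study-specific questions are exploratory and only summarised descriptively.

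**How many subjects.** The document has no discontinuation rate, so these rates are assumptions applied to the planned 9400:
- 10%: 0.10 × 9400 = 940
- 20%: 0.20 × 9400 = 1880
- 30%: 0.30 × 9400 = 2820

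**How far the contrast could move.** Let d_A and d_P be the proportions off IP in the albiglutide and placebo arms at a visit, and let g be the amount (in SD units) by which subjects off IP score below those still on it, taken as equal in both arms. Each arm's mean over all randomised subjects is its on-IP mean minus d × g. Hence

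on-IP contrast − all-randomised contrast = g × (d_A − d_P).

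- d_A = d_P (10%, 20% or 30%): difference 0, for any g.
- d_A = 30%, d_P = 20%, g = 0.25: 0.25 × 0.10 = 0.025 SD.
- d_A = 30%, d_P = 20%, g = 0.50: 0.50 × 0.10 = 0.050 SD.

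For scale, 1:1 allocation gives 4700 per arm. With 30% and 20% off IP, 3290 and 3760 remain. The unadjusted standard error is √(1/3290 + 1/3760) = 0.024 SD if all of them answer. The shift is then about one to two standard errors, though small as an effect size.

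All values of d and g are illustrative. Reversing d_A and d_P reverses the sign.

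**The case against.** The best defence is that Table 2 is a deliberate, specific rule. Table 1 points to it. Section 4.4.1 has discontinuers complete the final-visit assessments when they stop, which explains the single mark. TRIM-D measures satisfaction with treatment, so dropping it after treatment stops is a tenable choice. On this reading an exception clause in Section 6.3.1.1 would settle the matter. It is fair that the intent cannot be proved. But Section 6.3.1.1 covers all subjects and names one exemption, which is not this one. The revision chronology describes Table 2 as an aid that puts existing text into a table, and that text (Section 4.5) returns discontinuers to the 8-monthly schedule without dropping any assessment. The rationale also does not reach EQ-5D, a generic health measure. Even if the omission is intended, the passages must be reconciled.

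Several stronger readings are tempting and are not supported:
- A reader might infer that the comparison is confined to subjects who tolerate albiglutide. Scores before stopping, and one set at stopping, are still collected. IP is stopped in both arms, and Section 4.4.2 also lists subject decision, low eGFR, pregnancy and site closure.
- A reader might infer a bias in favour of albiglutide. That needs more discontinuation on albiglutide, or a different relation between stopping and score by arm. The protocol gives neither, and Section 3.3 calls both doses generally well tolerated.
- A reader might infer that the ANCOVA uses observed scores only. Section 8.3.6.5 does not say so and leaves further detail to the analysis plan.

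It also stands that the consequence is limited: these endpoints are secondary or exploratory and have no multiplicity control.

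**Conclusion.** The point holds as an inconsistency in the current text with a real but bounded consequence. For TRIM-D, Table 2 contradicts Section 6.3.1.1 at the 8-monthly and final clinic visits. For EQ-5D it leaves a gap against the planned each-visit comparison. Followed as written, Table 2 makes those comparisons rest essentially on subjects still on IP.

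The size is unknown. The 940 to 2820 subjects without a scheduled questionnaire depend on an assumed 10% to 30% discontinuation. The shift of 0.025 to 0.05 SD depends further on an assumed 10-point difference in discontinuation between arms and an assumed gap of 0.25 to 0.5 SD; with equal discontinuation and an equal gap it is zero. Bias is therefore possible, not shown, and its direction is open. The primary MACE analysis is unaffected. The correction should be made because the loss cannot be repaired at the analysis stage and the visits already take place.

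**What to change.** In Table 2, mark patient-reported outcomes in the 8-monthly clinic-visit column and the final study clinic visit column, so that it agrees with Section 6.3.1.1. In Section 8.3.6.5, state that these scores enter the TRIM-D and EQ-5D ANCOVA whether or not the subject is on IP. The section does not now exclude them; the sentence removes doubt.

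The cost is two table cells and one sentence, carried by a protocol amendment, plus a small questionnaire burden at visits already scheduled. It is not a complete remedy. Subjects who cannot attend and are followed by telephone under Table 2 would still have no questionnaire data, and visits that have already passed without a questionnaire cannot be recovered.

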6.1. Critical Baseline Assessments

Disease, and therapy history, including cardiovascular medical history/risk factors will be assessed at Baseline. Investigators are encouraged to implement lifestyle modifications and adjust or initiate the appropriate pharmacotherapy throughout the study as recommended by current locally followed therapeutic cardiovascular and diabetes guidelines for participants in the study. Screening and randomisation can occur at the same visit depending on availability of information to determine eligibility of the subject to enter the study.

6.2. Safety

The following sections provide further detail on the safety assessments. Planned time points for all safety assessments are listed in the Time and Events Table ([Table 1](#)). Unscheduled visits will occur as medically necessary. Detailed procedures for obtaining each assessment are provided in the SRM.

Safety endpoints are described in [Section 2](#) and will include monitoring of cardiovascular events ([Section 6.2.1](#)), deaths, AEs of special interest ([Section 6.2.3](#)), clinically significant microvascular events ([Section 6.2.4](#)), SAEs and AEs leading to discontinuation of investigational product.

Liver chemistry stopping and follow-up criteria and AEs are described in [Section 4.4.3](#) and [Appendix 3](#).

6.2.1. Cardiovascular Events

Events referred to the CEC by the investigator as potential endpoints or transient ischemic attacks (TIAs) will not be collected or reported as SAEs, regardless of the adjudication outcome ([Section 6.2.2](#))¹. These events will be reviewed by an Independent Data Monitoring Committee ([Section 9.8](#)).

The CEC will review and adjudicate the following clinical events:

Myocardial infarction

Stroke

Unstable angina requiring hospitalization

Hospitalization for heart failure

Sudden cardiac death

TIA

¹ There is one exception to this statement. Per requirement of the Mexican Ministry of Health, all events referred to the CEC by Mexican investigators will also be submitted as SAEs to the Mexican Ministry of Health.

In addition, all clinical events submitted for adjudication and all other SAEs with a fatal outcome will be reviewed and adjudicated to classify the cause of death as cardiovascular or non-cardiovascular.

When the local investigator reported event and the CEC decision on the nature of the event differ, the CEC's decision will be considered final. The detailed descriptions of the endpoint (and TIA) definitions necessary for adjudication are contained within the CEC Charter (available on request). The guiding principle will be the "2014 ACC/AHA Key Data Elements and Definitions for Cardiovascular and Stroke End Point Events for Clinical Trials" [ACC/AHA, 2014] and the "Third Universal Definition of Myocardial Infarction" endorsed by the European Society of Cardiology (ESC), the American College of Cardiology Foundation (ACCF), the American Heart Association (AHA), and the World Heart Federation (WHF) [Thygesen, 2012].

Source documentation required to support the adjudication of the events is described in the SRM. Recording of potential endpoint and TIA events in the eCRF and submission of source documentation will be required for clinical events meeting reporting criteria whether or not an endpoint event is suspected by the investigator.

6.2.1.1. Other CV Events

GSK has identified other CV events of special interest for all clinical studies. Investigators will be required to fill out event specific data collection tools for the following cardiovascular events which meet SAEs criteria or are non-serious events that result in discontinuation of investigational product:

Arrhythmias (other than atrial fibrillation/flutter, see Section 6.2.3)

Valvulopathy

Pulmonary hypertension

Peripheral arterial thromboembolism

Deep venous thrombosis/pulmonary embolism

Revascularisation (other than urgent revascularisation for unstable angina, a component of a secondary endpoint)

This information should be recorded in the specific cardiovascular eCRF within one week.

6.2.2. Adverse Events (AE) and Serious Adverse Events (SAEs)

The definitions of an AE or SAE can be found in [Appendix 5](#).

The investigator or site staff will be responsible for detecting, documenting and reporting events that meet the definition of an AE or SAE.

For this study events of myocardial infarction, stroke, unstable angina requiring urgent revascularization, hospitalization for heart failure, TIA and sudden cardiac death will not be collected or reported as AEs or SAEs. These events will be collected separately,

subjected to blinded adjudication by an independent CEC using prespecified diagnostic criteria, and reported separately (Section 6.2.1.1). All other events that meet serious criteria as defined in [Appendix 5](#) should be reported as SAEs.

All events with an outcome of death will be adjudicated to classify the cause of death as specifically cardiovascular or non-cardiovascular. Any event resulting in death should be reported as a SAE unless the event is myocardial infarction, stroke, unstable angina w/ urgent revascularization, Heart failure, TIA or sudden cardiac death which the protocol specifies are not to be collected as adverse events.

The study will not collect all non-serious AEs. Non-serious AEs leading to discontinuation of investigational product and non-serious AEs of special interest (see Section 6.2.3) will be collected.

Any events not specifically addressed above should be reported as an AE or SAE according to the definitions in [Appendix 5](#).

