2. OBJECTIVES AND ENDPOINTS

| Objectives | Endpoints |
|--|--|
| Primary | |
| To assess the effect of albiglutide with respect to MACE when added to glycaemic standard of care versus standard of care alone | 
Time to first occurrence of MACE (cardiovascular death, myocardial infarction, or stroke)
 
The primary analysis will be non-inferiority. If the pre-specified non-inferiority criterion is met then superiority testing will be performed¹
 |
| Secondary | |
| To supplement the primary objective by further characterization of the effects of albiglutide on cardiovascular outcomes | 
 • Time to first occurrence of the following: 
 ▪ MACE or urgent revascularisation for unstable angina ▪ The individual components of the primary endpoint ▪ Cardiovascular death or hospitalization due to heart failure |
| To evaluate the effects of albiglutide on metabolic management of type 2 diabetes | 
 • Time to initiation of insulin of more than 3 months duration for those subjects not treated with insulin at study start • Time to initiation of prandial insulin in those subjects on basal insulin at study start • The proportion of subjects achieving glycaemic control (HbA1c \leq 7.0% at final assessment) with no severe hypoglycaemic incidents and weight gain $<$5% of body weight • The time to first occurrence of a clinically important microvascular event (see Section 6.2.4) • Change in HbA1c • Change in body weight • Patient reported outcomes from TRIM-D/EQ5D |
| To evaluate the safety of albiglutide | 
 • All cause mortality • Non-fatal SAEs • AEs leading to discontinuation of investigational product • AE of special interest (see Section 6.2.3) • Change in eGFR calculated using MDRD formula • Change in blood pressure and heart rate |
| Exploratory | |
| To evaluate patient reported experience of diabetes treatment | 
 • Patient reported outcomes from study specific questionnaire |

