4.4.1. Early Discontinuation of Investigational Product

If a subject chooses to discontinue investigational product between scheduled face-to-face visits they should be encouraged to contact the investigator site by telephone. Subjects should first be counselled to consider temporary discontinuation of investigational product prior to choosing to discontinue investigational product permanently, unless the reason for discontinuation is one of those listed below (Reasons for Discontinuation of Investigational Product). If the discontinuation is permanent, the subject should be asked to attend the clinic as soon as possible to complete the assessments as for the final study visit (see Table 1) and then continue in the study for follow-up. The procedures for follow-up for a subject who permanently discontinues treatment with investigational product prior to the study end are given in Section 4.5.

In all cases, reasons for discontinuation of investigational product and the date of last dose will be recorded.

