4.4.2. Reasons for Discontinuation of Investigational Product

Any subject experiencing the following will be required to discontinue investigational product:

AE:

Pancreatitis, acute or chronic.

Pancreatic cancer.

MTC or other thyroid C-cell neoplasia. In subjects where a treatment emergent thyroid nodule is identified, if serum calcitonin is measured at the discretion of the Investigator (e.g., per local guidelines) and found to be >100 ng/L this should prompt further investigation for MTC and potential interruption or discontinuation of investigational product until diagnosis has been resolved.

Liver chemistry abnormalities exceeding the threshold criteria outlined in Section [4.4.3](#)

Severe allergic/hypersensitivity reactions that are considered by the investigator to be attributable to investigational product or without a likely alternative aetiology.

Other AE which, in the opinion of the investigator precludes continuation of dosing. eGFR<15ml/min/1.73m² (Section [4.4.4](#)) or the need for renal replacement therapy.

Subject becomes pregnant during the study.

Need for chronic use of a prohibited concomitant medication (Section [5.6.2](#))

Decision by subject or proxy.

Sponsor terminated study.

Investigator site closed and subject was unable to transfer to another investigative site.

[figure not shown]
If investigational product is discontinued, the subject should continue in the study and be followed until the final study visit as detailed in Section [4.5](#).

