8.3.6.4. Other Safety Analyses

Subject demographics, medical history, prior and concomitant medications, vital sign measurements, laboratory values, physical examination assessments, will be summarized by treatment group using descriptive statistics.

For continuous variables, these summaries will include sample size, mean, median, standard deviation, minimum, and maximum. For categorical variables, the summaries will include frequencies and corresponding percentages.

For SAEs, AEs leading to permanent IP withdrawal and AEs of special interest, the number and percentage of subjects, total number of events and incidence density will be presented by treatment group and overall at the SOC and Preferred Term (PT) level. Relative Risk and its 95% CI may also be presented on a targeted basis. The time to first occurrence of specific events will be summarized.

All cause mortality will be summarized by treatment group and analyzed using a Cox PH model similarly as the-primary endpoint.

All events sent to CEC (including TIAs) will be summarized.

Pancreatitis events will be adjudicated by the independent Pancreatitis Adjudication Committee. The information for investigator reported pancreatitis events and its adjudication results will be summarized.

Further analysis details will be provided in the RAP.

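### The safety endpoint counting AEs that lead to stopping study drug omits stops caused by the cardiovascular events that Section 6.2.2 bars from AE reporting

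*Protocol*

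**What the plan says.** Section 6.2.2 names "events of myocardial infarction, stroke, unstable angina requiring urgent revascularization, hospitalization for heart failure", together with TIA and sudden cardiac death, and takes them out of AE and SAE reporting ("hospitalization for heart failure, TIA and sudden cardiac death will not be collected or reported as AEs or SAEs"). They are collected on their own forms and sent to blinded adjudication.

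Section 6.2.1 adds that events the investigator refers to the CEC "will not be collected or reported as SAEs, regardless of the adjudication outcome". Its one exception is submission to the Mexican health ministry.

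Section 2 lists "AEs leading to discontinuation of investigational product" among the safety endpoints. Section 8.3.6.4 sets out the table: "For SAEs, AEs leading to permanent IP withdrawal and AEs of special interest, the number and percentage of subjects", with event totals and incidence density, by system organ class and preferred term. For adjudicated events the same section says only that "All events sent to CEC (including TIAs) will be summarized".

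On stopping drug, Section 4.4.2 includes "Other AE which, in the opinion of the investigator precludes continuation of dosing" among its reasons, and Section 4.4.1 states: "In all cases, reasons for discontinuation of investigational product and the date of last dose will be recorded".

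**The concern.** An event that may not be recorded as an AE cannot be counted as an AE that led to discontinuation. A subject taken off drug because of a stroke or a heart-failure admission would have an adjudication record and a recorded reason for stopping, but no AE record to feed the discontinuation table.

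This endpoint is where a reader looks to learn how many subjects stopped treatment because something happened to them. In a population chosen for established cardiovascular disease, cardiovascular events are a foreseeable cause of stopping. Leaving them out makes the count too low in each arm, and any difference between arms in such stops would not show in this table.

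Sites may also differ. One may respect Section 6.2.2 and enter no AE; another may enter one so that its reason for stopping has something to refer to. The endpoint would then be measured unevenly as well as incompletely.

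**Working it through.** **Text check**

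1. *Does the bar reach AEs, or only SAEs?* Section 6.2.2 covers both. The later statement in that section that non-serious AEs leading to discontinuation are collected does not rescue the listed events, because they are not to be collected as AEs at all. Its closing catch-all applies only to events not already addressed, and these are addressed.
2. *Is there an exception for events that stop treatment?* None in 6.2.1 or 6.2.2. By contrast, Section 6.2.1.1 asks for dedicated forms for other cardiovascular events, such as arrhythmia or valvulopathy, if they are serious or cause discontinuation. Section 6.2.2 points to 6.2.1.1 for the separate reporting of the listed events, but 6.2.1.1 does not cover them.
3. *Does the schedule route them into the endpoint?* Table 2 has separate rows, at the visit after permanent discontinuation, for MACE assessment and for AEs leading to discontinuation. Under 6.2.2 the listed events belong to the first row only.
4. *Does another planned output recover them?* The summary of CEC events in 8.3.6.4 has no stated breakdown by whether drug was stopped.
5. *Are the data lost?* No. Section 4.4.1 has the reason and last-dose date recorded for every discontinuation.
6. *Which unstable angina is meant?* Section 6.2.2 exempts cases needing urgent revascularisation and sends every other serious event to SAE reporting. Section 6.2.1 refers unstable angina requiring hospital admission to the CEC and exempts referred events from SAE reporting. For a subject admitted without urgent revascularisation, the two sections give different answers.

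**Scale**

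The protocol gives no figure for this omission. The inputs that it does give are 611 first MACE and 9400 subjects (Section 8.2.1). The 611 reproduces: for a margin of 1.3, two-sided alpha 0.05, 90% power and 1:1 allocation, events = 4 × (1.960 + 1.282)² / (ln 1.3)² ≈ 611.

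Two further inputs are my assumptions and are not in the protocol: *f*, the share of first MACE that are non-fatal (50% to 80%), and *s*, the share of those subjects who stop drug because of the event (2% to 20%).

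Omitted subjects = 611 × *f* × *s*

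| *f* | *s* | Subjects | % of 9400 |
|---|---|---|---|
| 0.50 | 0.02 | 6.1 | 0.07 |
| 0.65 | 0.05 | 19.9 | 0.21 |
| 0.65 | 0.10 | 39.7 | 0.42 |
| 0.80 | 0.20 | 97.8 | 1.04 |

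Two things push against each other. The 611 is an intent-to-treat count and includes events after drug had already been stopped, which cannot cause a stop; that lowers the figure. Heart-failure admission, TIA and unstable angina are not in MACE and would raise it, though some of those subjects also have a MACE.

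**The case against.** The best defence is that keeping endpoint events out of AE reporting is a deliberate and legitimate choice, and that the endpoint simply follows that convention. That stands for the SAE exemption. It does not explain why a discontinuation endpoint should inherit the exemption without saying so.

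A second point is that 6.2.2 governs how an event is collected and reported, not whether it meets the Appendix 5 definition of an AE. An investigator can therefore still stop drug and give an AE as the reason. Nor is 4.4.2 a closed list, since Section 5.3 allows a discretionary stop after unblinding, and the eCRF reason list is not in the document. This stands: one cannot say that the protocol leaves no usable reason for such a stop. But the planned table is by coded term and needs an AE record, which 6.2.2 does not allow.

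Third, details are left to the analysis plan, which could tabulate stops by recorded reason. It could, and that would close the gap. But the protocol itself fixes both the unit of the endpoint and the exclusion, so an analysis plan that applied them faithfully would reproduce the omission.

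A reader might also infer that a cardiovascular harm of the drug would be hidden. The documents do not support that. Infarction, stroke and cardiovascular death form the primary endpoint; heart-failure admission and urgent revascularisation for unstable angina are in secondary endpoints; and the data monitoring committee sees all cardiovascular event data about every 6 months. An excess of events would show there. What would not show is the excess of treatment stops that they caused.

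**Conclusion.** The point holds for one listed safety endpoint and its table. Read literally, Sections 2, 6.2.2 and 8.3.6.4 together omit permanent discontinuations caused by the exempted cardiovascular events, and the count is too low in both arms to the extent that such stops occur. The direction follows from the text. The size does not: roughly 6 to 98 subjects from MACE alone rests on the two assumed shares and on taking every non-fatal first MACE as occurring on drug.

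It is tempting to express the gap as a percentage of all event-driven discontinuations. That needs an overall discontinuation rate, which the protocol does not give, so no such percentage is supportable. It would also be too broad to say that all unstable angina is barred from AE reporting: 6.2.2 bars only cases needing urgent revascularisation, and 6.2.1 bars SAE reporting of referred events without mentioning AEs. The primary inference and the adjudicated endpoints are untouched.

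**What to change.** In Section 8.3.6.4, define the table as permanent discontinuation of investigational product because of (a) an AE or (b) an event referred to the CEC, on separate lines and by arm. Basing (b) on referral also captures stops for events that the committee does not confirm.

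Let the recorded reason identify a CEC-referred event, either through the eCRF reason list or by a few words beside the recording sentence in Section 4.4.1. Add nothing to the list in Section 4.4.2: it is headed as events that require discontinuation, so an entry there would read as a new mandatory stopping rule. The SAE exemption can stay.

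Sections 6.2.1 and 6.2.2 must be reconciled on which unstable angina events are exempt from AE and SAE reporting.

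The cost is one extra table line and one eCRF reason code. The reason and last-dose date are already collected, so little or no new data collection is needed.
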